13.1.2 PRE-CAE® TOTAL CORNEAL FLUORESCEIN STAINING (ORA CALIBRA® SCALE)

Pre-CAE® fluorescein staining will be graded using the Ora Calibra® Corneal and Conjunctival Staining Scale. The Ora Calibra® Corneal and Conjunctival Staining Scale ranges from 0 to 4 (half grade increments may be used), where grade 0 = none, 1 = trace, 2 = mild, 3 = moderate, and 4 = severe. Staining will be graded in the inferior, superior, corneal, temporal and nasal regions. The total corneal fluorescein staining score is the sum of the scores from the inferior, corneal and superior regions.

Pre-CAE® total corneal fluorescein staining will be analyzed similarly to pre-CAE® inferior fluorescein staining. Pre-CAE® total corneal fluorescein staining changes from baseline in the study eye will be displayed graphically in a bar chart with standard error bars by visit and treatment group based on the ANCOVA analysis. The ANCOVA models, including the ANCOVA model used in the MCMC analysis, will include terms for baseline total corneal staining score, baseline ICCS and baseline eye dryness score as covariates and treatment group as a factor in the model.

LOCF and MCMC imputation will be performed for each region separately, prior to calculating the total corneal fluorescein staining score. The following random number seed values will be used for the MCMC imputations: 62521 + S for inferior region, 38751 + S for central region, 91121 + S for superior region, 22252 + S for temporal region, and 83620 + S for nasal region, where S = 1 for Stage 1 data analysis, S = 2 for Stage 2 data analysis, and S = 3 for analysis of the combined Stage 1 and Stage 2 data.

13.1.3 PRE-CAE® TOTAL CORNEAL FLUORESCEIN STAINING (OXFORD SCALE)

The Oxford scale ranges from 0 to 5 for the corneal region with higher scores indicating greater staining.

Pre-CAE® total corneal fluorescein staining (Oxford scale) will be analyzed similarly to pre-CAE® inferior fluorescein staining (Ora Calibra® scale). The ANCOVA models, including the ANCOVA model used in

the MCMC analysis, will include terms for baseline total corneal staining score (Oxford scale), baseline inferior corneal staining score (Ora Calibra® scale) and baseline eye dryness score as covariates and treatment group as a factor in the model. Pre-CAE® total corneal fluorescein staining changes from baseline in the study eye will be displayed graphically in a bar chart with standard error bars by visit and treatment group based on the ANCOVA analysis.

The random number seed values that will be used for the MCMC imputations are given by $61521 + S$, where $S = 1$ for Stage 1 data analysis, $S = 2$ for Stage 2 data analysis, and $S = 3$ for analysis of the combined Stage 1 and Stage 2 data.

13.1.4 PRE-CAE® EYE DRYNESS (VISUAL ANALOG SCALE)

In the VAS assessment, the subject will be asked to rate each of several ocular symptoms due to ocular dryness by placing a vertical mark on a 100 mm horizontal line to indicate the level of discomfort. A score of 0 corresponds to “no discomfort” and 100 corresponds to “maximal discomfort”.

Eye dryness will be assessed by VAS and analyzed similarly to pre-CAE® inferior fluorescein staining (Ora Calibra® scale). The ANCOVA models, including the ANCOVA model used in the MCMC analysis, will include terms for baseline eye dryness (VAS) and baseline inferior corneal staining score (Ora Calibra® scale) as covariates and treatment group as a factor in the model. Eye dryness changes from baseline will be displayed graphically in a bar chart with standard error bars by visit and treatment group based on the ANCOVA analysis.

The random number seed values that will be used for the MCMC imputations are given by $65521 + S$, where $S = 1$ for Stage 1 data analysis, $S = 2$ for Stage 2 data analysis, and $S = 3$ for analysis of the combined Stage 1 and Stage 2 data.

13.1.5 PRE-CAE® TOTAL OSDI

The OSDI® is assessed on a scale of 0 to 100, with higher scores representing greater disability. The OSDI® asks the following 12 questions at the subject level:

Have you experienced any of the following during the last week:

- 1) Eyes that are sensitive to light?
- 2) Eyes that feel gritty?
- 3) Painful or sore eyes?
- 4) Blurred vision?
- 5) Poor vision?

Have problems with your eyes limited you in performing any of the following during the last week:

- 6) Reading?
- 7) Driving at night?
- 8) Working with a computer or bank machine (ATM)?

9) Watching TV?

Have your eyes felt uncomfortable in any of the following situations during the last week:

10) Windy conditions?

11) Places or areas with low humidity (very dry)?

12) Areas that are air conditioned?

OSDI[®] will be collected for both eyes pre-CAE[®] at each visit. The 5-unit scale for responses to the OSDI[®] is given by the following: 0 = None of the time, 1 = Some of the time, 2 = Half of the time, 3 = Most of the time and 4 = All of the time. The total OSDI[®] score is calculated by the following:

$$\text{OSDI}^{\circledast} = \frac{(\text{sum of scores}) \times 25}{\# \text{ of questions answered}}$$

Note that the number of questions answered in the denominator should exclude those questions with a response of "N/A".

Pre-CAE[®] Total OSDI[®] will be analyzed similarly to pre-CAE[®] inferior fluorescein staining (Ora Calibra[®] scale). The ANCOVA models, including the ANCOVA model used in the MCMC analysis, will include terms for baseline Total OSDI[®], baseline inferior corneal staining score (Ora Calibra[®] scale) and baseline eye dryness score as covariates and treatment group as a factor in the model. Pre-CAE[®] Total OSDI[®] changes from baseline will be displayed graphically in a bar chart with standard error bars by visit and treatment group based on the ANCOVA analysis.

LOCF and MCMC imputation will be performed for total OSDI score; separate imputations will not be created for each individual question score. The random number seed values that will be used for the MCMC imputations are given by 67521 + S, where S = 1 for Stage 1 data analysis, S = 2 for Stage 2 data analysis, and S = 3 for analysis of the combined Stage 1 and Stage 2 data.

13.2 Secondary Analyses

The continuous and ordinal secondary efficacy variables collected at each visit will be summarized descriptively (n, mean, SD, median, min and max) by visit and treatment group. Change scores from pre- to post-CAE[®] will be calculated as post-CAE[®] score minus pre-CAE[®] score. Changes from baseline will also be summarized descriptively by visit and treatment group. No imputation will be performed for secondary efficacy variables. Analyses will be performed on the mITT population with observed data only. All secondary measures will also be presented in subject listings.

The following secondary efficacy endpoints will be tested:

- Unanesthetized Schirmer's Test
- TFBUT

- Conjunctival Redness Score
- Fluorescein Corneal Staining (Ora Calibra® scale)
- Fluorescein Corneal Staining (Oxford scale)
- Lissamine Green Conjunctival Staining (Oxford scale)
- Ocular Discomfort Score
- Ocular Discomfort & 4-Symptom Questionnaire
- VAS
- OSDI
- SANDE

13.2.1 UNANESTHETIZED SCHIRMER'S TEST

Unanesthetized Schirmer's Test will be assessed on both eyes at all visits. Visit 1 and 5 assessments will be pre-CAE®. The Schirmer's test strip will be placed in the lower temporal lid margin of each eye. After 5 minutes, the test strip will be removed and the length of the moistened area will be recorded in millimeters (mm) for each eye. Lower values indicate less tears produced in the eye.

Unanesthetized Schirmer's Test will be summarized by treatment group and visit using quantitative summary statistics. Change from baseline will be also summarized.

Pairwise two-sample t-tests will be employed to compare treatment and vehicle means at each visit and time point. The differences in means, two-sided 95% CIs for the difference in means and p-values will be reported. Wilcoxon rank sum tests will also be conducted. Analyses will be performed on the mITT population with observed data only.

Changes from baseline will be compared between treatment groups using ANCOVA models that adjust for baseline value, baseline inferior corneal staining (Ora Calibra® scale) and baseline eye dryness (VAS). The differences in means, two-sided 95% CIs for the difference in means and p-values will be reported. T-tests and Wilcoxon rank sum tests will also be conducted. Analyses will be performed on the mITT population with observed data only.

Binary clinical cure variables will be defined by visit for Schirmer's test ≥ 5 mm, Schirmer's test ≥ 10 mm and Schirmer's change from baseline ≥ 5 mm, and will summarized by visit using number of subjects, frequency counts and percentages. Treatment groups will be compared pairwise with vehicle using Pearson's chi-square test or Fisher's exact test if the expected cell count is less than 5 in 25% or more of the cells. In addition, the proportion of responders will be compared between treatment groups using the Cochran-Mantel-Haenszel method stratifying by baseline ICSS (≤ 1.5 , > 1.5) and baseline eye dryness (< 60 , ≥ 60). For the Cochran-Mantel-Haenszel analysis of the combined Stage 1 and Stage 2 data, the study Stage will also be included as a stratification factor.

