7.3 Inclusion Criteria

1. Male or female, 18 years of age or older at screening visit
2. Provide written informed consent
3. Be willing and able to follow instructions and participate in all study assessments and visits
4. Best-corrected visual acuity (BCVA) of 20/100 or better (Snellen equivalent), using the logarithm of the minimum angle of resolution (LogMAR) in each eye at Visits 1 and 2
5. Must have patient reported history of dry eye for at least 6 months prior to Visit 1
6. Use of non-prescription artificial tears for the symptoms of DED within the 30 days preceding the screening visit and willing to suspend use of artificial tears for the study duration
7. Corneal fluorescein staining score ≥ 2 according to the Ora Calibra[®] scale in at least one region in at least one eye at the screening Visit 1 (Pre-CAE[®]) and Visit 2
8. Conjunctival redness score ≥ 1 according to the Ora Calibra[®] Conjunctival Redness for Dry Eye Scale in at least one eye at Visit 1 (Pre-CAE[®]) and Visit 2
9. Eye dryness score ≥ 40 (0-100 VAS scale in both eyes) at Visit 1 (Pre-CAE[®]) and Visit 2
10. Total Ocular Surface Disease Index (OSDI) score > 18 at Visit 1 (Pre-CAE[®]) and Visit 2
11. In the same eye at Visits 1 and 2, subjects must have:
 - a. Inferior corneal fluorescein staining score ≥ 0.5 according to the Ora Calibra[®] Corneal and Conjunctival Staining Scale for Grading of Fluorescein Staining, Pre-CAE[®] at Visit 1
 - b. Schirmer's Tear Test without anesthesia ≥ 1 and ≤ 10 mm

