12.4.6 Secondary Efficacy Analyses

Continuous secondary efficacy variables (see [Section 8.1.2](#)) and changes from baseline in these measures will be summarized as described in [Section 12.4.1](#), and analyzed by visit using ANCOVA as described for the primary efficacy analyses.

Binary clinical cure variables representing clinical cure will be defined by visit for TBUT ≥ 10 , Schirmer's test ≥ 10 mm, Total OSDI < 18 , and Ocular Discomfort Score = 0. These binary variables will be summarized as described in [Section 12.4.1](#). Additionally, within each treatment group, shift tables for complete treatment response (yes/no) in the study eye relative to baseline will be presented for each variable.

The Cochran-Mantel-Haenszel test, stratified by baseline inferior corneal staining score (ICCS, > 1.5 and ≤ 1.5) and eye dryness score (≥ 60 and < 60) will be used to compare treatments with respect to the proportion of cured patients. Pairwise comparisons will be performed for each AXR-159 treatment group versus vehicle. Two-sided confidence intervals (95%) will be provided for the differences between treatments. The confidence intervals will be constructed using the normal approximation to the binomial distribution.

The secondary efficacy analysis will use the mITT population with observed data only.

Details of additional secondary efficacy analyses will be provided in the statistical analysis plan.

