8.1 Unit of Analysis

Safety endpoints will be analyzed for both eyes. For efficacy endpoints, the unit of analysis will be the study eye, or the “worst eye,” as defined by the following:

Study Eye/Worst Eye: Eyes are eligible for analysis if they meet all of the inclusion criteria. In the case that both eyes are eligible for analysis, the study eye will be the eye with worse (higher) inferior corneal staining score (Ora Calibra® scale) on Day 1. If the inferior corneal staining score is the same in both eyes, then the right eye will be selected as the study eye.

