13.2.2 TEAR FILM BREAK-UP TIME (TFBUT)

TFBUT will be measured at all scheduled visits on both eyes. Both pre- and post-CAE® assessments will be made at Visits 1 and 5. For each eye, two measurements will be recorded in seconds and averaged unless the two measurements are >2 seconds apart and are each <10 seconds, in which case, a third measurement will be taken and the two closest of the three will be averaged and used for analyses. If the differences between two sequential pairs of measurements are the same, e.g., 3, 6, 9 seconds, then the median of the three readings will be used for analysis.

TFBUT will be summarized by treatment group, visit and time point (pre- and post-CAE®) using quantitative summary statistics. Change from baseline will be also summarized.

Pairwise two-sample t-tests will be employed to compare treatment and vehicle means at each visit and time point. The differences in means, two-sided 95% CIs for the difference in means and p-values will be reported. Wilcoxon rank sum tests will also be conducted. Analyses will be performed on the mITT population with observed data only.

Changes from baseline will be compared between treatment groups using ANCOVA models that adjust for baseline value, baseline inferior corneal staining (Ora Calibra® scale) and baseline eye dryness (VAS). The differences in means, two-sided 95% CIs for the difference in means and p-values will be reported. T-tests and Wilcoxon rank sum tests will also be conducted. Analyses will be performed on the mITT population with observed data only.

Binary clinical cure variables will be defined by visit for TFBUT ≥ 5 s, TFBUT ≥ 10 s, and TFBUT change from baseline ≥ 5 s, and will be summarized by visit using number of subjects, frequency counts and percentages. Treatment groups will be compared pairwise with vehicle using Pearson's chi-square test or Fisher's exact test if the expected cell count is less than 5 in 25% or more of the cells. In addition, the proportion of responders will be compared between treatment groups using the Cochran-Mantel-Haenszel method stratifying by baseline ICSS (≤ 1.5 , > 1.5) and baseline eye dryness (< 60 , ≥ 60). For the Cochran-Mantel-Haenszel analysis of the combined Stage 1 and Stage 2 data, the study Stage will also be included as a stratification factor.

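### The absolute-threshold 'clinical cure' variables have no baseline condition, so study eyes already at the threshold on Day 1 and unchanged are counted and tested as cured

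*SAP*

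**What the plan says.** Entry: Protocol 7.3, item 11b, requires "Schirmer's Tear Test without anesthesia ≥ 1 and ≤ 10 mm" in the same eye at Visits 1 and 2. SAP 8.1 ties the analysed eye to this: "Eyes are eligible for analysis if they meet all of the inclusion criteria". The study eye therefore starts treatment with a Schirmer value between 1 and 10 mm, both ends included.

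Outcome: SAP 13.2.1 says "Binary clinical cure variables will be defined by visit for" three rules, namely "Schirmer's test ≥ 5 mm, Schirmer's test ≥ 10 mm and Schirmer's change from baseline ≥ 5 mm", and 13.2.2 names "TFBUT ≥ 5 s, TFBUT ≥ 10 s, and TFBUT change from baseline ≥ 5 s". Later parts of SAP 13.2 add redness = 0, staining clearance (score = 0) and one-unit improvement by region, ocular discomfort = 0, and total OSDI below 18. Protocol 12.4.6 has a shorter list: Schirmer and TBUT at 10, OSDI below 18 and discomfort = 0. The 5 mm and 5 s rules appear only in the SAP.

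Test: each active group is compared with vehicle by chi-square or Fisher's exact test, and by CMH stratified on baseline inferior staining and baseline eye dryness (plus stage in the combined data). No absolute-threshold definition asks where the eye stood on that measure at baseline. Protocol 12.4.6 also plans yes/no shift tables against baseline, which the SAP lists as Tables 14.2.20.1.1 to 14.2.20.1.3.

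**The concern.** A cure should describe a change of state. Where the entry range and the cure range overlap, the rule counts two kinds of patient together: those who crossed the threshold on treatment, and those who were never below it. The reported rate then overstates improvement in both arms, vehicle included.

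Neither planned test separates the two groups, because baseline status on the tested measure is not a stratum. The continuous analysis of the same measure in SAP 13.2.1 does adjust for its baseline value, so the binary analysis is the exception. The practical risk is that a high 'cure' rate is read as response, or carried into the planning of a later trial.

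**Working it through.** **1. Which variables overlap with entry (Protocol 7.3 against SAP 13.2)**

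| Cure variable | Entry limit | Can it be met at Day 1? |
|---|---|---|
| Schirmer ≥ 5 mm | 1 to 10 mm | Yes, by any eye at 5 to 10 mm |
| Schirmer ≥ 10 mm | 1 to 10 mm | Only at exactly 10 mm |
| TFBUT ≥ 5 s, ≥ 10 s | None | Possible |
| Ocular discomfort = 0 | None on this scale | Possible |
| Staining clearance, non-inferior regions | No regional guarantee | Possible |
| Redness = 0 | ≥ 1 in at least one eye | Only if the fellow eye met the criterion |
| Ora Calibra inferior clearance | ≥ 0.5 | No |
| OSDI < 18 | > 18 | No |
| Gains of ≥ 5 mm or ≥ 5 s; staining change ≤ -1 | Not relevant | No, improvement is required |

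**2. The plan's own figure.** Protocol 12.1 and SAP 5 give 80% power for 93 against 60 patients (difference 0.35, SD 0.75, two-sided 0.05). The standard error is 0.75 × √(1/60 + 1/93) = 0.124, and Φ(0.35/0.124 − 1.96) = 80.5%; the noncentral t gives 80.0%. The counts match 10% dropout: 103 × 0.9 = 92.7 and 67 × 0.9 = 60.3. The figure reproduces. It concerns inferior staining, and no sample-size figure is given for the cure variables, so 93 and 60 are borrowed below.

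**3. Effect on the reported rate.** Let f be the share already at threshold on Day 1, r the share of those still there at the visit, and p the new-cure rate among the rest.

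Reported rate = f·r + (1 − f)·p

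Difference between arms = f·(r_active − r_vehicle) + (1 − f)·(p_active − p_vehicle)

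None of f, r or p is in the documents; all values here are assumptions. An even spread over the integers 1 to 10 mm gives f = 6/10 for the 5 mm rule and 1/10 for the 10 mm rule. New-cure rates are set at 20% (vehicle) and 40% (active).

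Power is Φ[(d − 1.96·SE₀)/SE₁], where d is the difference, SE₀ is pooled and SE₁ unpooled. With r = 100% in both arms:

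| f | Reported, vehicle / active | Difference | Power, all patients | Power, below threshold at Day 1 only |
|---|---|---|---|---|
| 0 | 20% / 40% | 20 points | 75% | 75% |
| 10% | 28% / 46% | 18 points | 61% | 70% |
| 30% | 44% / 58% | 14 points | 39% | 59% |
| 60% | 68% / 76% | 8 points | 20% | 36% |

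In the last row d = 0.08, SE₀ = 0.0736 and SE₁ = 0.0748, so Φ(−0.86) = 0.195. There, 60/68 = 88% of vehicle 'cures' and 60/76 = 79% of active 'cures' were at threshold before treatment. With r = 80% in both arms the differences are the same, and power for all patients is 62%, 39% and 17% at f = 10%, 30% and 60%.

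**4. Does the dilution survive unequal retention?** Keep f = 60% and the 20% and 40% new-cure rates.

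- Retention 80% (vehicle) and 90% (active): reported 56% and 70%, a 14-point difference. Power is 42% for all patients and 36% for the restricted test.
- Retention 60% and 80%: reported 44% and 64%, the full 20 points. Power is 68% against 36%.

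The risk difference is diluted only when treatment affects retention less than it affects new crossings. The restricted test can lose power even when some dilution remains, because its denominator is smaller.

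**The case against.** Several points against this have force.

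- **The shift tables already show baseline status.** They do, and a careful reader could recover the new-cure rate from them. They are descriptive, however, and leave the tested proportions unchanged.
- **Change-based variables and baseline-adjusted ANCOVA are planned.** Correct. They measure improvement properly, and the sponsor is not without a sound analysis of Schirmer or TFBUT.
- **The protocol's endpoint list already says 'proportion of patients with'.** Also correct, but Protocol 12.4.6 and SAP 13.2 revert to 'clinical cure'.
- **The worst case is not a protocol endpoint.** The protocol names 10 mm, where overlap is one value. At f = 10% the illustrated power gap is 61% against 70%, much smaller than for the SAP's 5 mm rule.
- **Restricting the denominator has its own faults.** It discards maintenance of response and selects low readings, so regression to the mean still produces some 'cures' in both arms. This stands, and is the reason to retain an all-patient comparison.

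A reader might infer that eyes already above threshold cannot show a treatment effect, so the contrast must be diluted and power lost. The documents do not support that. Such an eye can fall below threshold, and treatment may prevent it. Step 4 shows the power ranking reversing with a 10-point retention benefit at f = 60%.

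**Conclusion.** The point holds for the absolute-threshold variables, and it is chiefly one of labelling and interpretation. It is certain for Schirmer ≥ 5 mm, marginal for Schirmer ≥ 10 mm, and possible for TFBUT ≥ 5 s and ≥ 10 s, ocular discomfort = 0 and non-inferior staining clearance. For these, the cure rate overstates improvement in both arms by an amount that cannot be known from the documents. The 68% and 76% illustration rests on an even baseline spread, full retention and assumed new-cure rates.

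Two wider readings are tempting and should be resisted. One is that every cure variable is flawed: OSDI < 18, Ora Calibra inferior clearance and the change-based variables are sound in this respect. The other is that the comparison is biased. Randomisation balances baseline responders in expectation, so type I error is not at issue. These are secondary endpoints in a study whose efficacy analyses SAP 8.5 calls exploratory, and the primary analyses are untouched. Loss of power is a conditional risk, not a finding.

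**What to change.** Before unmasking, amend SAP 13.2 for each affected variable:

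1. Define cure as not meeting the threshold at Day 1 and meeting it at the visit. Report and test it in study eyes that did not meet the threshold at baseline.
2. Relabel the all-patient figure as the proportion at or above threshold (or the proportion with score = 0). Keep it as a supportive comparison, with baseline threshold status added as a CMH stratum.
3. Leave OSDI < 18, Ora Calibra inferior clearance and the change-based variables as they are.

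The cost is SAP wording, one denominator filter and some extra table rows; no new data or visits are needed. The main downside is a smaller denominator for the cure test. At f = 60% it falls from 93 and 60 to about 37 and 24, and power can be lost if treatment also improves retention. The extra stratum also thins the CMH cells: the combined-stage analysis would go from 2 × 2 × 2 = 8 strata to 16, and few eyes may fall in the already-met stratum for Schirmer ≥ 10 mm.

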13.2.2 TEAR FILM BREAK-UP TIME (TFBUT)

TFBUT will be measured at all scheduled visits on both eyes. Both pre- and post-CAE® assessments will be made at Visits 1 and 5. For each eye, two measurements will be recorded in seconds and averaged unless the two measurements are >2 seconds apart and are each <10 seconds, in which case, a third measurement will be taken and the two closest of the three will be averaged and used for analyses. If the differences between two sequential pairs of measurements are the same, e.g., 3, 6, 9 seconds, then the median of the three readings will be used for analysis.

TFBUT will be summarized by treatment group, visit and time point (pre- and post-CAE®) using quantitative summary statistics. Change from baseline will be also summarized.

Pairwise two-sample t-tests will be employed to compare treatment and vehicle means at each visit and time point. The differences in means, two-sided 95% CIs for the difference in means and p-values will be reported. Wilcoxon rank sum tests will also be conducted. Analyses will be performed on the mITT population with observed data only.

Changes from baseline will be compared between treatment groups using ANCOVA models that adjust for baseline value, baseline inferior corneal staining (Ora Calibra® scale) and baseline eye dryness (VAS). The differences in means, two-sided 95% CIs for the difference in means and p-values will be reported. T-tests and Wilcoxon rank sum tests will also be conducted. Analyses will be performed on the mITT population with observed data only.

Binary clinical cure variables will be defined by visit for TFBUT ≥ 5 s, TFBUT ≥ 10 s, and TFBUT change from baseline ≥ 5 s, and will be summarized by visit using number of subjects, frequency counts and percentages. Treatment groups will be compared pairwise with vehicle using Pearson's chi-square test or Fisher's exact test if the expected cell count is less than 5 in 25% or more of the cells. In addition, the proportion of responders will be compared between treatment groups using the Cochran-Mantel-Haenszel method stratifying by baseline ICSS (≤ 1.5 , > 1.5) and baseline eye dryness (< 60 , ≥ 60). For the Cochran-Mantel-Haenszel analysis of the combined Stage 1 and Stage 2 data, the study Stage will also be included as a stratification factor.

